4.3 JUSTIFICATION FOR DOSE AND FORMULATION

TQ Formula will be administered as an oral dose daily. The dose planned in this study is 3 g per day (3 500mg capsules to be taken twice daily). The dosing decision is based on the mechanism of action, the pharmacology in non-human studies (the drug has extensive pre-clinical pharmacokinetic and pharmacodynamic testing) and human data for completed studies across a number of therapeutic indications (see references in toxicity section above). The proposed dose of 3 g per day has been used in a number of human trials reporting side effects ranging from absence of any side effects to mild side effects; otherwise, the drug has been well tolerated. Mahdavi et al. conducted a double-blind placebocontrolled randomized clinical trial to determine the effects of NS oil combined with a calorie-restricted diet on systemic inflammatory biomarkers in obese women. 90 volunteer obese women were enrolled. The intervention group received 3 g/day NS oil soft gel capsules (one capsule, three times a day, 30 minutes before each main meal), and the placebo group received similar amounts of sunflower oil as a placebo for eight weeks. Subjects reported no side effects during the intervention except mild gastrointestinal problems [81]. In a study by Bamosa et al., patients with type 2 diabetes mellitus were randomly divided into 3 groups to receive Nigella Sativa seed extracts at 1 gm, 2 gms and 3 gms per day respectively for 12 weeks. In the study, generally, the three doses of Nigella sativa were well tolerated with only three patients who experienced a mild epigastric discomfort that settled down after taking the capsules post meals [68]. In a study by Datau et al. performed on 39 centrally obese men assigned to receive NS seeds (3 g/day for 3 months) or placebo, subjects reported subjective complaints related to central obesity (body ache, weakness, sleeplessness, belching, decreased libido). All subjective complains reported by subjects in the treatment group disappeared in the first week of the study, but they all still persisted in the control group through the end of the study. [65].

Enteric coated formulation

To mask the after taste/unpleasant taste of black seed oil in TQ Formula, enteric coating will be applied on the drug (and the placebo). Previous clinical studies using fish oil have shown enteric coating to be safe with the added benefit of improving compliance and enhancing gastric absorption by transient protection against gastric acidity [112].

Dosing Modifications

Based upon data from previous studies using blackseed oil capsules, the doses proposed in this protocol are within the maximum tolerated doses. However, dose reductions will be allowed per protocol as below (Table 4.3.1).

If a patient experiences a Grade 3 or greater drug-related AE after a dose of blackseed capsules upon evaluation per protocol, then the next dose will not be administered. The patient may receive additional doses of blackseed capsules, at the discretion of the PI, if the Grade 3 or greater event has resolved or has been reduced sufficiently as assessed by the treating PI prior to administration of the additional doses of blackseed capsules and dose reduction will be allowed as per Table 4.3.1 below.

Table 4.3.1: Dose modifications

Agent	Starting Dose (0 Dose Level)	-1 Dose Level	-2 Dose Level
Blackseed Oil Capsules/Placebo	500 mg, 3 capsules, orally twice a day (total 3g daily)	500 mg, 2 capsules, orally twice a day (total 2g daily)	500 mg, 1 capsule, orally twice a day (total 1g daily)

For Grade 3 or greater treatment related toxicity that cannot be controlled with symptomatic treatment within 48 hours, such as nausea and/or vomiting that can be controlled by antiemetics or diarrhea that can be controlled by anti-diarrheal medicines, the dose level will be decreased to dose level -1. Similarly, patients who develop Grade 3 treatment related toxicity that cannot be controlled with symptomatic treatment within 48 hours at dose level -1 will have further decrease in dosage to dose level -2. Finally, patients who develop Grade 3 treatment related toxicity that cannot be controlled with symptomatic treatment within 48 hours at dose level -2 will discontinue therapy. If the patient experiences significant toxicity requiring a dose reduction, the patient will remain at the lower dose level for subsequent cycles, i.e., dose re escalation is not allowed.

Patients should terminate study treatment if further reduction is indicated beyond the -2 level.

Treatment may be delayed up to 10 days to allow for recovery from treatment-related toxicities. If the patient has not recovered after a 10 day delay, all study treatment will be discontinued. Participant will remain on study for safety follow up per schedule of assessments.

Resuming therapy may not be allowed until treatment-related toxicities have resolved to baseline, unless the toxicities are considered by the Investigator unlikely to develop into serious or lifethreatening events. In this case, treatment may be continued at the same dose without reduction or interruption.

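### Section 4.3 requires the dose to be held after a Grade 3 or greater drug-related event, yet a later paragraph permits uninterrupted full dosing with no grade limit

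*Protocol*

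**What the plan says.** All the text is in protocol section 4.3, under Dosing Modifications. The SAP has no dosing rules.

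- **Hold.** After a Grade 3 or greater drug-related event, "then the next dose will not be administered". Further doses are at the PI's discretion, provided "the Grade 3 or greater event has resolved or has been reduced sufficiently as assessed by the treating PI". At that point "dose reduction will be allowed as per Table 4.3.1 below".
- **Reduction.** Grade 3 or greater treatment-related toxicity that is not controlled within 48 hours requires a drop from 3 g/day to level -1 (2 g/day in Table 4.3.1). The trigger reads "toxicity that cannot be controlled with symptomatic treatment within 48 hours, such as nausea and/or vomiting that can be controlled by antiemetics", and diarrhea is treated in the same way. The next step down applies to "patients who develop Grade 3 treatment related toxicity that cannot be controlled with symptomatic treatment within 48 hours at dose level -1". The wording for level -2 is parallel and leads to discontinuation.
- **Delay and exception.** Treatment may be delayed for up to 10 days. The default for restarting is strict: "Resuming therapy may not be allowed until treatment-related toxicities have resolved to baseline". That default gives way to a judgment by the site, being worded to apply "unless the toxicities are considered by the Investigator unlikely to develop into serious or lifethreatening events". The section then adds: "In this case, treatment may be continued at the same dose without reduction or interruption".

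**The concern.** The hold and the 48-hour reduction are mandatory and carry no exception. The later paragraph covers treatment-related toxicity of any grade and lifts both actions on the investigator's judgment. A site facing Grade 3 vomiting that is attributed to the capsules, but judged unlikely to become serious, finds one paragraph telling it to withhold and another permitting full dose.

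What is at stake is safety conduct and exposure in the patients these rules exist to protect. Deviation status is also unclear: section 10.1.10 allows no waivers, and a site using the exception for a Grade 3 event follows one paragraph and breaks another. The primary intention-to-treat analysis is little affected.

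**Working it through.** The plan gives no figure to reproduce. The check is mainly a comparison of rules, followed by simple dose arithmetic.

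**1. Can one event meet both rules?** Yes. Section 8.3.2 defines a serious event by its outcome, not its grade. Section 8.3.3.1, for events outside the CTCAE, separates severe from serious. A Grade 3 event can therefore be judged unlikely to become serious.

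**2. The rules side by side, for a first event at the starting dose**

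| Situation | Hold and reduction rules | Exception |
|---|---|---|
| Next dose after a Grade 3+ drug-related event | Must be withheld | May be given |
| Controlled within 48 hours | May resume at 3 g/day; reduction is optional | 3 g/day with no gap |
| Uncontrolled at 48 hours | Must drop to 2 g/day | 3 g/day may continue |
| Grade limit | Grade 3 or greater | None stated |

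**3. Duty against permission.** The first column is a duty and the second a permission. Withholding complies with both. Continuing complies only with the exception and breaches the hold.

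**4. Readings that would remove the conflict**
- *The exception is meant only for toxicity below Grade 3.* This is plausible as an intention, but no grade is written.
- *The exception applies only after a delay.* Treatment already delayed cannot be continued without interruption.
- *The exception is an investigator override.* The section does not say so. The hold rule already gives the PI discretion, but only once the event has resolved or sufficiently reduced.

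**5. Dose arithmetic.** Inputs: 500 mg capsules, 3 per dose, twice daily for 14 days; level -1 is 2 g/day (section 4.3); missed doses are not made up (section 6.1.2).

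- One dose = 3 × 500 mg = 1.5 g. Full course = 28 × 1.5 g = 42 g.
- Controlled within 48 hours: the minimum difference is one dose, 1.5 g.
- Uncontrolled at 48 hours and not sufficiently reduced: 0 of the 4 doses due under the hold, against 4 × 1.5 g = 6 g under the exception. After that, 2 g/day against 3 g/day.

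Illustrative course totals follow. The onset days are assumptions, and the first two rows also assume dosing restarts at exactly 48 hours.

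| Event after last dose of | Hold | Total under hold and reduction | Difference from 42 g |
|---|---|---|---|
| Day 2 | 48 hours | 6 + 0 + 10 × 2 = 26 g | 16 g; 16/42 = 38% |
| Day 10 | 48 hours | 30 + 0 + 2 × 2 = 34 g | 8 g; 8/42 = 19% |
| Day 2 | 10 days (the maximum delay) | 6 + 0 + 2 × 2 = 10 g | 32 g; 32/42 = 76% |

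The third row shows how far the total moves with the length of hold alone. These are grams of capsule contents; only the active arm receives black seed oil.

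**6. The trigger wording.** The rule applies when symptomatic treatment fails, but its examples are nausea, vomiting and diarrhea that respond to treatment. Read literally, the examples fall outside the rule they illustrate. At levels -1 and -2 the words extending the trigger above Grade 3 are missing, so a Grade 4 event is not literally covered by those two steps.

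**The case against.** The best reply is that a specific, mandatory rule for Grade 3 or greater displaces a general permission, so a careful investigator would hold the dose and breach nothing. That is right as far as it goes, and it rules out one tempting inference: that two sites could treat the same event differently with both following the protocol. The site that continues full dose is in breach of the hold rule. What remains is that the section expressly offers that site the permission and states no order of precedence.

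The practical risk is also limited. Section 4.3 describes side effects at 3 g/day as absent to mild, section 6.1.2 anticipates no dose-limiting effects, and treatment lasts 14 days. The investigator may stop treatment for any adverse event (section 7.2), liver criteria exist (section 8.5), and a medical monitor has oversight (section 10.1.6). These limit harm but do not say which rule governs.

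The trigger faults are minor. The examples look like a slip, since the governing clause is clear. The narrower grade at lower levels leaves only a small gap: the hold is not tied to a dose level, and treatment ends if reduction beyond -2 is indicated. Both are still worth correcting in the same edit.

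A reader might also see conflicting standards for resuming treatment, sufficient reduction in one place and return to baseline in the other. These can largely be read together, because both allow re-dosing before full resolution on the investigator's judgment.

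**Conclusion.** The conflict holds as a fault in the written rules: section 4.3 makes withholding, and reduction at 48 hours, mandatory for Grade 3 or greater drug-related events, and separately permits full uninterrupted dosing for a class of toxicity that includes such events. The firm size is at least one 1.5 g dose per affected patient, and more if the event is uncontrolled at 48 hours. The documents give no expected Grade 3+ rate, onset day or length of hold, so no total is determined, and few patients are likely to be affected.

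Two stronger inferences are not supported:

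- **That the 38% and 19% differences are the expected effect.** They are illustrations only. They assume a restart at exactly 48 hours, which the hold rule does not guarantee for an event still uncontrolled.
- **That the enrollment halt in section 9.4.4 is affected.** An attributable Grade 3+ event unresolved at 48 hours in the first 12 patients counts toward the three-patient limit whether or not dosing continued.

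The correction should be made because it removes an express permission to dose through a Grade 3 or greater drug-related toxicity.

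**What to change.** Amend section 4.3 as follows:

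1. Limit the exception on continuing at the same dose to treatment-related toxicity below Grade 3.
2. State that the hold and reduction rules govern all Grade 3 or greater drug-related toxicity.
3. Reword the examples to nausea or vomiting not controlled by antiemetics, and diarrhea not controlled by anti-diarrheal medicines.
4. Use Grade 3 or greater as the trigger at the starting dose and at levels -1 and -2.

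The cost is a wording amendment to one section, with no new visits or data and no effect on sample size or power.

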4.4 END OF STUDY DEFINITION

A participant is considered to have successfully completed the study if he or she has completed all phases of the study including the last visit shown in the Schedule of Activities (SoA), Section 1.3. An end of study form will be completed in EDC. Participants who terminate early will also have an end of study form completed.

5 STUDY POPULATION

5.1 INCLUSION CRITERIA

In order to be eligible to participate in this study, an individual must meet all of the following criteria:

1. Provision of signed and dated informed consent form
2. Stated willingness to comply with all study procedures and availability for the duration of the study
3. Male or female, aged 18 and over, presenting with recent mild to moderate clinical symptoms of Covid-19 infection (per FDA guidance – see appendix 3)
4. Positive COVID-19 infection confirmed with a rapid antigen test at screening and confirmed with a RT-PCR test at baseline
5. A score of ≥ 3 on a minimum of 2 symptoms on the Modified FLU-PRO Plus
6. Ability to take oral medication and be willing to adhere to the dosing regimen (Twice a day – BID for 14 days)
7. For females of reproductive potential: negative pregnancy test at screening and use of highly effective contraception method during study participation and for an additional 4 weeks after the end of study drug administration
8. For males of reproductive potential: use of condoms or other methods to ensure effective contraception with partner during study participation
9. Agreement to adhere to Lifestyle Considerations (see section 5.3) throughout study duration

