13 APPENDIX 2 – MODIFIED FLU-PRO PLUS©QUESTIONNAIRE

Participant ID:

Participant Initials: _____ Date: _____ / _____ / _____

Modified FLU-PRO Plus[®]

People experience Covid-19 in different ways. We would like to know about the symptoms you have been experiencing during the past 24 hours. For each symptom, please mark one box under the response that best matches your experience. Mark the "Not at all" box if you did not have that symptom in the past 24 hours.

Please complete this questionnaire each evening.

What time is it? _____ AM/PM (please circle)

Please rate the extent to which you had each symptom during the past 24 hours.

Not at all A little bit Somewhat Quite a bit Very much

Sore or painful throat					
Difficulty swallowing					

Trouble breathing					
Chest congestion					
Chest tightness					
Dry or hacking cough					
Wet or loose cough					

Felt nauseous (feeling like you wanted to throw-up)					
Stomach ache					

Felt dizzy					
Head congestion					
Headache					

Participant ID:

Participant Initials: _____ Date: _____ / _____ / _____

Please rate the extent to which you had each symptom during the past **24 hours**.

	Not at all	A little bit	Somewhat	Quite a bit	Very much
Lack of appetite					
Sleeping more than usual					
Body aches or pains					
Weak or tired					
Chills or shivering					
Sneezing					
Coughing					
Coughed up mucus or phlegm					
Loss of smell					
Loss of taste					

In the past **24 hours**, **how often** have you had any of the following symptoms?

	0 times	1 time	2 times	3 times	4 or more times
How many times did you vomit?					
How many times did you have diarrhea?					

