# BOSS-Covid-19 Study (BOSS-001)

1. To evaluate if treatment with 3 g TQ Formula (500 mg per capsule, 3 capsules BID) given orally on outpatient basis can significantly reduce median time to sustained clinical response compared to placebo in participants with COVID-19 infection treated in the outpatient setting. Sustained clinical response is defined as a reduction of scores to </= 2 on all symptoms of the Modified FLU-PRO Plus and should be remaining </= 2 for at least three days.
2. To evaluate the safety and tolerability of TQ Formula (500 mg oral capsule, 3 capsules BID) when given to participants with COVID-19 infection

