# BOSS-Covid-19 Study (BOSS-001)

## 5.3.2 Primary Analyses

Primary estimand-1 is defined to be the difference of median time to sustained clinical response between participants taking 3 g TQ Formula (500 mg per capsule, 3 capsules BID) and participants taking placebo regardless of whether or not they actually receive their assigned therapy (ITT) and assuming that their hospitalization and treatment discontinuation rates will be similar. Possible intercurrent events for this estimand can be, though expected to be quite rare, hospitalization (i.e., transitioning from outpatient status to inpatient status) and treatment discontinuation, both of which may lead to potential missing data or change in the primary measures. The study participants will be reminded to submit their Modified FLU-PRO Plus questionnaires even after these intercurrent events to avoid missing data as much as practically possible. Hospitalization-free, while-on-study and per-protocol treatment versions of the above estimand will also be considered within each population definitions above.

Median time to sustained clinical response for the treatment and placebo arms will be estimated using the Kaplan-Meier method and Log-rank test will be utilized to compare the time to sustained clinical response distributions between the two study arms using LIFETEST procedure in SAS Version 9.4 ® (SAS Institute, Cary, North Carolina, USA). Events will be defined as cases that attain sustained clinical response while on study and time to event will be calculated as the days from the date of symptoms onset to the date that all symptoms are below Level-2 ('A little bit') on the Modified FLU-PRO Plus questionnaire. Patients who do not attain to clinical response while on study will be censored on Day-21 or on the day they are off study before Day-21 due to other reasons.

Although all analyses will be conducted based on the intent-to-treat principle, sensitivity analyses based on the adherence to the protocol regimen will also be carried out for the primary as well as secondary objectives. Sensitivity analyses will also include hospitalization-free, while-on-study, and per-protocol treatment cohorts as described above.

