## 7.9 List of Tables, Figures and Listings

Demographic characteristics table, AE and SAE tables, tables of Covid-19 test results both from the rapid test and RT-PCR, the distribution statistics table for the viral load assessments, any other secondary objective measure tables. Modified FLU-PRO Plus assessments will be shown graphically as time series plot with a reference line at Level-2 ('Somewhat') where the y-axis will show the scale from 'Not at all (Level-0)' to 'Very much (Level-4)'.

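### The symptom form has no numeric key and the SAP labels Level 2 in two ways, so the entry cut-off of 3 and the response cut-off of 2 can each mean one of two adjacent categories

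*Protocol*

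**What the plan says.** **Entry.** Protocol 5.1, criterion 5, requires "A score of ≥ 3 on a minimum of 2 symptoms on the Modified FLU-PRO Plus". SAP 3.3.1 repeats it. Neither attaches a word to the number 3. The footnote to the Schedule of Activities says that the screening questionnaire is completed on site to decide eligibility.

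**Form.** Protocol Appendix 2 heads its severity columns "Not at all A little bit Somewhat Quite a bit Very much", with a tick box under each and no codes. The two count items (vomiting, diarrhoea) have columns running from 0 to 4 or more times.

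**Response.** SAP 3.6 states: "Sustained clinical response is defined as a reduction of scores to </= 2 on all symptoms of the Modified FLU-PRO Plus". It adds a persistence condition: this level must be held for three days or more. SAP 3.2 and 4.1.1 agree with this. The protocol gives the same cut-off without the three-day condition.

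**Level 2 in the event rule.** SAP 5.3.2 ends the time to event on "the date that all symptoms are below Level-2 ('A little bit') on the Modified FLU-PRO Plus questionnaire".

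**Level 2 in the plots.** SAP 7.9 calls for "a reference line at Level-2 ('Somewhat') where the y-axis will show the scale from 'Not at all (Level-0)' to 'Very much (Level-4".

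**A third event wording.** Protocol 9.4.2 runs the time to event until symptoms have resolved to zero.

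**The concern.** A number decides who may be randomised, and another number on the same scale decides when the primary event has occurred. Neither can be applied without knowing which box carries which code. The form does not say, and the two SAP sections that attach a word to Level 2 attach different ones.

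Two things are at stake. First, with 2–4 centres, sites that assume different codings would admit patients one category apart in severity, and source verification would have no written rule for checking criterion 5 against the ticked boxes. Second, the same ambiguity moves the primary event by one category. A key chosen at the analysis stage can settle the second problem but cannot change who was admitted.

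**Working it through.** **Inputs.** Entry cut-off, 3 or more on at least two symptoms (Protocol 5.1). Response cut-off, 2 or less on all symptoms (SAP 3.2, 3.6, 4.1.1). The event rule's 'below Level 2' (SAP 5.3.2). The five categories in order (Protocol Appendix 2). The two labels for Level 2 (SAP 5.3.2 and 7.9).

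**Step 1: the two codings.** If Level 2 is 'A little bit', the second of five categories, the scale runs 1–5. If Level 2 is 'Somewhat', the third, it runs 0–4.

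| Category | 0–4 | 1–5 |
|---|---|---|
| Not at all | 0 | 1 |
| A little bit | 1 | 2 |
| Somewhat | 2 | 3 |
| Quite a bit | 3 | 4 |
| Very much | 4 | 5 |

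So 3 is 'Quite a bit' or 'Somewhat', and 2 is 'Somewhat' or 'A little bit'.

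**Step 2: entry against response, all four combinations.**

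| Screening | Analysis | Entry (≥3) | Response (≤2) | In both, at ≤2 | In both, at <2 |
|---|---|---|---|---|---|
| 0–4 | 0–4 | Quite a bit or worse | Somewhat or better | none | none |
| 1–5 | 1–5 | Somewhat or worse | A little bit or better | none | none |
| 0–4 | 1–5 | Quite a bit or worse | A little bit or better | none; 'Somewhat' is in neither | none |
| 1–5 | 0–4 | Somewhat or worse | Somewhat or better | 'Somewhat' | none |

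The overlap occurs in one of four combinations at ≤2, and in none of four if the event is taken as below Level 2. In the one case it concerns only a patient with at least two items at 'Somewhat' and nothing worse.

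**Step 3: the event wordings under each coding.**

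| Wording | 0–4 | 1–5 |
|---|---|---|
| 2 or less (SAP 3.2, 3.6, 4.1.1) | Somewhat or better | A little bit or better |
| Below Level 2 (SAP 5.3.2) | A little bit or better | Not at all |
| Zero (Protocol 9.4.2) | Not at all | no such score |

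Under 0–4 coding the three wordings set three different bars. Settling the code therefore does not by itself settle the event.

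**Step 4: which coding the documents favour.** For 0–4: the axis in SAP 7.9, written out at both ends; the zero in Protocol 9.4.2; and the count items, whose columns start at 0. For 1–5: only the parenthesis in SAP 5.3.2.

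**Step 5: the plan's own figure.** The stated power is 81.5% with 20 per arm and a 10-day difference from a 16-day placebo median (16 against 6 days). Assuming exponential times, the hazard ratio is 6/16 = 0.375. Freedman's formula with all 40 patients having the event gives Φ(√40 × 0.625/1.375 − 1.96) = Φ(0.915) = 82.0%, close to the stated value. No input to it depends on how the form is coded, so it neither supports nor weakens this point.

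**The case against.** The strongest reply is that there may be only one coding. On a 0–4 scale the category just below Level 2 is 'A little bit', so the parenthesis in SAP 5.3.2 could explain the phrase 'below Level 2' rather than name Level 2. Read that way, SAP 5.3.2 and 7.9 agree on 0–4, as do the other signals in step 4. That reading is possible, and it is a good reason to prefer 0–4. It does not close the matter. It leaves the event rule at 'A little bit' or better, while the stated endpoint under the same coding is 'Somewhat' or better.

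It can also be said that SAP 6.3 has questionnaires, including the screening one, entered on online forms that may carry codes. They may, but their coding is not in either document.

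A reader might go further and infer that patients can be enrolled already in response, with an event on Day 1 in both arms and a measurable loss of power. The documents do not support this as a consequence of the double label. It needs sites to score 1–5 while the analysis scores 0–4 with ≤2, which no text says will happen. Response is worded as a reduction and must hold for three days, so worsening within three days prevents it. The three-day rule is not a complete safeguard, because SAP 3.2 counts to the first day on which all symptoms are 2 or less, so a stable patient could still be dated to that first day. Nor would such events share one time value, since the clock starts at symptom onset (SAP 5.3.2, Protocol 9.4.2) or at testing (SAP 3.2), not on Day 1.

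**Conclusion.** The inconsistency is real and lies in a decision threshold. Without a key, the entry and response cut-offs can each fall on one of two adjacent categories, a shift of one in five. This rests only on the text of Appendix 2, SAP 5.3.2 and SAP 7.9, taking the parenthesis in 5.3.2 in its natural sense as the label of Level 2.

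The overlap between entry and response is a conditional risk: one of four coding combinations, one category, and none under the below-Level-2 wording. Used consistently, either coding keeps the two apart. Sizing the risk would require the share of patients whose worst symptoms are 'Somewhat' and the share of screenings scored 1–5. The documents give neither, so no frequency and no power loss should be attached to it.

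**What to change.** 1. Adopt one coding. The 0–4 scale is the only one written out at both ends, and it fits the count items and the zero in Protocol 9.4.2. If the sponsor means 1–5, SAP 7.9 has to change instead.
2. Print the code beside each category on the Appendix 2 form and in the electronic diary, and state the codes for the two count items.
3. State criterion 5 and the response definition in words plus code. Under 0–4: entry, at least two symptoms at 'Quite a bit' (3) or 'Very much' (4); response, every symptom at 'Somewhat' (2) or lower for at least three days. Under 1–5: entry, at least two symptoms at 'Somewhat' (3) or worse; response, every symptom at 'A little bit' (2) or lower for at least three days.
4. Correct the Level 2 label in SAP 5.3.2 or 7.9 to match. Changing the label alone is not enough: also reconcile 'below Level 2' in SAP 5.3.2 and 'zero' in Protocol 9.4.2 with the endpoint of 2 or less on all symptoms, sustained for at least three days.

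The cost is wording in Protocol 5.1, 9.4.2 and Appendix 2 and in the SAP (3.3.1, 5.3.2, 7.9 and the response definitions), plus a diary label. It needs no extra patients or visits. It should be settled before sites screen.
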